5. STUDY DEVICE

5.1 Study Device Information

The ITN delivers small electrical currents to the inner cavity of the nose, gently activating nerves that stimulate the body's natural tear production system.

The device consists of four distinct parts (Figure 1):

1. A reusable Base Unit, which produces the electrical stimulation waveform.
2. A disposable Tip Assembly that inserts into the nasal cavity and stimulates the target intranasal tissue.
3. A reusable Cover to protect the Tip Assembly.
4. A Charger, which recharges the battery inside the Base Unit.

Figure 1: The TrueTear® Intranasal Neurostimulator (ITN) components.

1. Base Unit

When activated, the base unit provides electrical pulses to the Tip Assembly. The strength of these pulses is controlled by two buttons, with five different levels available, indicated by the number of illuminated LEDs on the base unit. The Base Unit can only be activated when a Tip Assembly is present. The base unit also records the use of the device, stimulation level and

Tufts Medical Center

duration, in internal memory. Upon return of the device, this information will be downloaded from the device and summarized as described in the Statistics section below.

2. Tip Assembly

The Tip Assembly is specially designed to allow the participant to easily apply stimulation to the target areas within the nose. The Tip Assembly connects to the Base Unit and contains a hydrogel (similar to the material used in contact lenses) that touches the inside of the nose to provide stimulation. The disposable Tip Assemblies are removed and replaced at least daily; a separate Cover can be used to protect the Tip Assembly when not in use.

3. Cover

The cover may be slipped over the top of the Base Unit and Tip Assembly between uses.

4. Charger

The Base Unit may be recharged by removing the Tip Assembly and placing it onto the Charger. Charging takes under 4 hours, and a green LED indicates that the process has completed.

5. Device Accountability

The investigator will be responsible for maintaining a device accountability log(s) that will track device usage for all study participants. Information tracked will include date of device receipt, lot and/or serial number, date of device usage or return (if applicable), subject ID, the occurrence of any device malfunctions or failures.

6. Labeling, Packaging, Storage, and Return or Disposal of Study Devices

All devices will be stored and maintained in accordance with package directions. Non-disposable devices should be returned to the Sponsor at the conclusion of the study. Used disposable devices should be discarded after use; unused disposable devices should be returned to the Sponsor at the conclusion of the study.

5.2 Study Device Compliance/Adherence

Directed questioning using the (Ocular Tolerability and Compliance Questionnaire – Appendix VI) will be administered by the investigator or research staff. Results on the participants' compliance and adherence to the study protocol and study device will be recorded on the paper case report form (CRF). During the study, all concomitant medication treatment regimens, ocular hygiene treatments (i.e., lid scrubs and warm compresses), or insertion of punctal plugs will be kept constant as permitted by accepted medical practice. If one of the aforementioned treatment regimens needs to be modified, the participant may be withdrawn based on the investigator's discretion.

Participants must be compliant with IVCM imaging on the study visit or they will be withdrawn. Subjects who are withdrawn may be replaced by new enrolled subjects to maintain the sample size.

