4.0 SUBJECT SELECTION

4.1. Subject Inclusion Criteria:

1. Age ≥ 22 .
2. Ability to consent to study.
3. Symptoms of neuropathic corneal pain for at least 3 months, such as burning, stinging, light sensitivity, discomfort or pain.
4. Positive *in vivo* confocal microscopy (IVCM) findings for NCP such as presence of microneuromas and decreased nerve density. The presence of positive IVCM findings serves in lieu of skin biopsies as proof of nerve injury.
5. Fifty percent or more relief of pain or discomfort after instillation of Proparacaine eye drops as measured by the Visual Analogue Scale (VAS).

4.2. Subject Exclusion Criteria:

1. Clinically significant acute ocular surface diseases, such as active infectious keratitis or recent ocular surgery in the past 3 months.
2. Chronic or recurrent epistaxis, coagulation disorders.
3. Nasal or sinus surgery or significant trauma to the nose.
4. Severe nasal airway obstruction or vascularized nasal polyps.
5. Cardiac demand pacemaker, implanted or wearable defibrillator, or other implanted electronic device in the head or neck.
6. Chronic or recurrent nosebleeds
7. Bleeding disorder or another condition that can lead to increased bleeding
8. Known hypersensitivity (allergy) to the hydrogel material that contacts the nasal mucosa
9. Disabling arthritis, neuropathy, or limited motor coordination affecting self-handling of the device.
10. Allergic to benzalkonium chloride (the Co-Investigators who administer the eye drops ask all patients if they are allergic to any eye drop preservatives before proceeding with the eye drops)

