6. BIOSPECIMEN COLLECTION (IF APPLICABLE)

6.1 Specimen preparation, handling, and shipping: N/A

6.2 Instruction for specimen preparation, handling and storage: N/A

6.3 Specimen shipment: N/A

6.4 Future use of stored specimens: N/A

7. STUDY PROCEDURES

7.1 Screening/Baseline Procedures

Prospective participants, as defined by the inclusion/exclusion criteria, will be considered for entry into this study. Concurrent enrollment of subjects who are participants in other studies will be allowed based on the investigator's discretion.

During the consent process, study design and treatment regimen will be discussed with each subject. Written informed consent will be obtained before any study specific procedures are performed. However, standard of care clinical information (such as: medical history, BCVA, TBUT, staining, and Schirmer's test) obtained during a subject's clinical visit within the previous 48 hours can be used during the screening visit to determine eligibility and as their baseline assessments.

The following evaluations and procedures will be performed for all subjects during the screening period:

- Written informed consent
- Record of current ocular and systemic medications
- Record of significant medical/surgical history in the past 5 years
- Record of demographic data, including date of birth, sex, and race/ethnicity
- Eye examination (best corrected visual acuity, slit-lamp biomicroscopy, intraocular pressure)
- Corneal fluorescein staining
- Conjunctival lissamine green staining
- Tear break-up time (TBUT)
- Corneal *in vivo* confocal microscopy (IVCM)
- Ocular Surface Disease Index (OSDI) questionnaire
- Ocular Pain Assessment Survey (OPAS) questionnaire
- IDEEL QoL Questionnaire
- The following evaluations and procedures will be performed for all subjects during the Enrollment/Baseline procedures (once the patient is confirmed to be eligible): Visual Analogue Scale (VAS) questionnaire before and after each of the five tests (filter glasses response, hyperosmolar saline response, cold saline response, proparacaine challenge test) Schirmer's test II (with anesthesia)

The description of the procedures is as follows:

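### Background treatment must be constant only during the study, not before it, so the effect of a recently started treatment can enter the secondary day-45 and day-90 changes as apparent ITN benefit

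*Combined protocol and SAP*

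**What the plan says.** The control over background treatment is in section 5.2: "During the study, all concomitant medication treatment regimens, ocular hygiene treatments" and punctal plugs "will be kept constant as permitted by accepted medical practice". If a regimen has to change on study, "the participant may be withdrawn based on the investigator's discretion". Nothing there concerns the time before entry.

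Section 4 has five inclusion and ten exclusion criteria. Two carry a time window: "Symptoms of neuropathic corneal pain for at least 3 months" and the exclusion for "recent ocular surgery in the past 3 months". Neither concerns drugs, drops or plugs, and there is no washout or run-in.

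At screening, section 7.1 asks for a "Record of current ocular and systemic medications", with no mention of start or last-change dates. The same section states: "Concurrent enrollment of subjects who are participants in other studies will be allowed based on the investigator's discretion".

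The trial is open-label with a single arm (section 3.1). Pain change is tested with a two-tailed paired t-test at 0.05, with no adjustment for background treatment (section 3.2). The primary endpoint is VAS change after ITN stimulation (section 10.1). VAS change over 45 and 90 days, and quality of life by OPAS and IDEEL, are secondary (section 10.2).

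**The concern.** Consider a patient who starts a pain medicine or an eye drop, or has plugs inserted, a week before baseline and continues unchanged. No rule in the protocol is broken. If that treatment takes weeks to act, pain falls between baseline and day 90 for a reason unrelated to the device.

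There is no comparison arm in which the same fall would appear, so the paired change includes it. Aims 2 and 3 (efficacy and longevity over 90 days, and quality of life) rest on those changes.

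The protocol already treats a change of regimen during the study as a possible ground for withdrawal, and it excludes recent ocular surgery. A regimen changed just before baseline threatens the 90-day comparison in much the same way as one changed just after, but only the second is addressed.

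**Working it through.** **Is the gap closed elsewhere?** Section 5.2 covers the study period only. Section 4 has windows for symptoms and ocular surgery but none for treatment. Section 7.1 lists current medications and medical/surgical history over five years, and sets no stability requirement. Section 3.2 has no adjustment, and section 10.4 (analysis population) is marked not applicable. The gap is not closed.

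**Which endpoints are exposed?** Section 10.2 lists days 45 and 90 separately, so the primary endpoint is read as the in-office response, which section 7.4 times at 1 and 3 minutes. A background effect that builds over weeks hardly moves a change measured over minutes. The exposed outcomes are the day-45 and day-90 VAS, OPAS and IDEEL changes.

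**Is there a plan figure to reproduce?** None bears on this point. The 25 patients for 80% power in section 10.3 correspond to a standardised paired effect of 0.584 (two-sided t). No baseline mean or SD of change is given, so that figure supplies no SD to use here.

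**Illustration of size.**

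Inputs from the documents: two-sided 0.05 paired t-test; n = 30 (section 10.3) or n = 45 (section 3.1).

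Assumed, because the documents give none of them: no ITN effect; SD of change 2 on a 10-point pain scale; k of n patients are recent starters whose pain later falls by d points on average; all others change by 0 on average; no other before-after bias.

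- Apparent mean ITN effect = (k/n) × d. For k = 6, n = 30, d = 2 this is 0.2 × 2 = 0.4 points; for d = 3 it is 0.6.
- False positive = significant at two-sided 0.05 in favour of ITN, so the nominal rate is 2.5%. Simulated rates:

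| n | Recent starters | d = 1 | d = 2 | d = 3 |
|---|---|---|---|---|
| 30 | 3 (10%) | 4% | 6% | 9% |
| 30 | 6 (20%) | 7% | 15% | 24% |
| 30 | 9 (30%) | 11% | 29% | 50% |
| 45 | 9 (20%) | 9% | 21% | 37% |

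**Analytic cross-check** (k = 6, n = 30, d = 2). The pooled SD is √(2² + 0.2 × 0.8 × 2²) = √4.64 = 2.154. The noncentrality is 0.4/2.154 × √30 = 1.017. The noncentral t with 29 degrees of freedom gives about 16.5%, against 15% simulated. The formula treats the number of starters as random, whereas the simulation fixes it, so a small difference is expected.

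At the same 20% share, the rate is higher with 45 patients than with 30. A larger sample makes the false attribution more likely.

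**The case against.** The strongest reply is one of proportion. This is an open-label pilot, and placebo response, regression to the mean and natural history enter the same paired change. With n = 30 and SD 2, an assumed 0.5-point non-specific improvement in every patient gives noncentrality 0.5/2 × √30 = 1.37 and a false-positive rate of about 26% with no recent starters at all. The 2.5% comparator is therefore not one this design would reach in practice, and a stability criterion would not restore it. That stands. The illustration isolates one source of bias and should not be read as the error rate the fix would recover. It also stands that the larger figures need a later fall of 1 to 1.5 SD in recent starters. At a 1-point fall the rate is only 4%–11%.

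A reader might infer more than the documents support:

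- **That the primary result is compromised.** It is measured within minutes and is little affected.
- **That start dates are not captured.** Section 7.1 does not ask for them, but the CRF fields are not shown and the medical record is source data (section 12.1), so dates may be recoverable.
- **That section 5.2 gives false assurance.** It limits itself to the study period and claims nothing about the time before entry.
- **That recruited patients usually have treatment changed around entry.** Nothing in the documents says how often this happens.
- **That no collected data could help.** The diary (Appendix VII) records symptoms before and after each use, and that contrast is far less exposed to a slow background effect. It is not, however, a named endpoint.

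None of this closes the gap. The other biases are inherent in a single-arm design, whereas this one can be reduced cheaply without a control arm.

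**Conclusion.** The point holds for the secondary day-45 and day-90 outcomes. A treatment started or changed shortly before baseline and then kept constant complies with the protocol, and its later effect is counted as ITN effect.

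The size is unknown. It depends on three quantities the documents do not give: the share of recent starters, their later improvement and the SD of change. Over the assumed ranges the effect on the false-positive rate runs from slight (three starters of 30, 1-point fall) to severe (nine of 30, 3-point fall). The case for acting rests on the gap in the rules and the low cost of closing it, and not on any one of those figures.

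**What to change.** 1. **Section 4:** add a criterion that background pain and ocular-surface treatments, including punctal plugs, have been unchanged for a stated period before baseline. The investigators should set and justify the length. The protocol's existing 3-month windows were set for symptom duration and ocular surgery, so they do not settle it.
2. **Section 7.1:** record the start or last-change date of each treatment with the medication list.
3. **Section 10.5:** add a sensitivity analysis of the day-45 and day-90 VAS, OPAS and IDEEL changes that excludes patients whose treatment began or changed within that period. Include patients already enrolled, as far as their dates can be recovered.

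This governs entry and analysis only and does not say how any patient should be treated. The cost is one criterion, one date field per treatment, one extra analysis and somewhat slower recruitment. If slower recruitment is unacceptable, items 2 and 3 alone would still show whether the later results depend on recent starters. Placebo response, regression to the mean and natural history remain, and the report should say so.

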3.0 STUDY DESIGN

3.1. Study Design Description

This study is a prospective, interventional, open-label, single arm, non-randomized trial treating 45 patients with peripheral or mixed neuropathic corneal pain at their baseline exam and following 45 days and 90 days of daily use with the TrueTear™ ITN device.

3.2 Statistical analysis:

Two-tailed paired sample t-test and Pearson correlation will be performed for pain intensity, and to assess associations between different quality of life scores. Statistical comparisons of the mean values between different groups based will be performed using ANOVA.

The normality of continuous variables will be tested with the Shapiro-Wilk test. All tests will be two tailed and statistical significance will be considered for p values of less than 0.05.

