Ocular Surface Disease Index (OSDI) questionnaire: (Appendix I) 12-item questionnaire designed to provide a rapid assessment of the symptoms of ocular irritation consistent with dry eye disease and their impact on vision-related functioning. The 12 items of the OSDI questionnaire are graded on a scale of 0 to 4, where 0 indicates none of the time; 1, some of the

Tufts Medical Center

time; 2, half of the time; 3, most of the time; and 4, all of the time. The total OSDI score is then calculated on the basis of the following formula: OSDI= [(sum of scores for all questions answered) x]/[(total number of questions answered) x 4].

Ocular Pain Assessment Survey (OPAS): OPAS Questionnaire (Appendix III): 27-item quantitative questionnaire designed to provide an assessment of the symptoms and quality of life effect of ocular pain. The 27 items of the OPAS questionnaire are graded on a scale of 0 to 10, or 10 to 100, where 0 indicates none and 10 or 100 indicate maximum. This questionnaire should take approximately 2-3 minutes to complete.

Visual Analogue Questionnaire: (Appendix IV) Symptoms of ocular comfort and dryness will be graded for each eye on a scale of 0-100, where 0=extremely uncomfortable, extremely dry and 100=excellent comfort, no dryness. An average rating will be provided for the morning, afternoon and evening. This questionnaire should take approximately 2-3 minutes to complete.

IDEEL QoL Questionnaire (Appendix V): This is a 27-item questionnaire, designed specifically for DED and is divided into three parts. It assesses the quality of life in three aspects of life for the previous 2 weeks: daily activities, work and feelings. The quality of life is assessed on a scale of 0-5, with zero being inability to do the activity. The score is calculated between 0 – 100 with higher scores indicating a better quality of life. This questionnaire should take about 5-10 minutes complete.

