7.2 Study Visit

The study will be performed in four visits. During the baseline visit, all patients will be evaluated using the flowchart (page 2). The first visit will include in-office testing of ITN and response to ITN. After 45 days (6 weeks \pm 1 week) and 90 days (3 months \pm 2 weeks) of using the ITN on a daily basis, the patients will return for follow-up visits. The same flowchart as for screening visit will be followed in these two visits (with the exception confocal microscopy on visit 2). Additionally, evaluation of diary for daily use (Appendix VII) and questionnaires regarding

Tufts Medical Center

tolerability and safety of device and any reduction in the use of concomitant pain medications will be assessed on these visits.

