7.4 Follow-up Procedures

Subjects will come back for a 1st visit after the screening visit; 2nd visit at 45 days (\pm 1 week) following the first visit, and 3rd visit following 90 days after the first visit (\pm 2 weeks). All of the procedures done at the baseline visit will be done in the 2nd and 3rd visits (see flowchart).

In addition, subjects will be asked about their usage of the ITN. Ocular safety and tolerability questionnaire (appendix VI) will be administered in the 2nd and 3rd visit. The subject will be asked to complete a diary every day to record any pain symptoms (Appendix VII). The subject will be asked to send their pain diary weekly to the study coordinator, in however method works for the subject to ensure compliance with the ITN. They will also need to bring the diary to each study visit, to ensure compliance.

Ocular Tolerability Questionnaire (Appendix VI): This questionnaire assesses tolerability of the ITN device. It assesses symptoms of discomfort in each eye after ITN use.

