7.6 Early Termination

If a subject withdraws or is withdrawn from the study prior to completion of all study visits, there will be no additional procedures performed

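### Withdrawing patients whose concomitant therapy changes, with no outcome follow-up and no analysis population, can bias the day-45 and day-90 results, mainly in favour of the device

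*Combined protocol and SAP*

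**What the plan says.** All references are to the combined protocol and SAP.

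- **Withdrawal and replacement (5.2).** Concomitant medication, lid hygiene and punctal plugs are to stay constant as far as accepted practice permits. "If one of the aforementioned treatment regimens needs to be modified", then "the participant may be withdrawn based on the investigator's discretion". Next comes "Subjects who are withdrawn may be replaced by new enrolled subjects to maintain the sample size", with no limit on how long the patient may already have been treated.
- **Design (3.1).** An "open-label, single arm, non-randomized trial treating 45 patients". The person deciding on withdrawal therefore knows how the patient is doing, and there is no control arm.
- **After withdrawal (7.6).** "there will be no additional procedures performed". Sections 8.1 and 9.3 continue adverse-event follow-up only.
- **Analysis (3.2, 10.4, 10.5).** A two-sided paired t-test at 0.05, with Pearson correlation and ANOVA. The analysis population in 10.4 is entered as not applicable. There is no rule for missing data and no sensitivity analysis.
- **Data before withdrawal (7.4 Follow-up Procedures, Appendix VII).** "The subject will be asked to send their pain diary weekly to the study coordinator". The diary includes daily items from the Ocular Pain Assessment Survey (OPAS). Nothing says whether diary data of withdrawn patients are analysed.
- **Reduced pain therapy as an outcome (7.2, 10.2, 10.5).** At the day-45 and day-90 visits "any reduction in the use of concomitant pain medications will be assessed on these visits". Section 10.2 lists such a reduction as a secondary outcome, and 10.5 uses it as a measure of effectiveness.
- **Endpoints (10.1, 10.2).** The primary is the change on the visual analogue scale (VAS) after ITN stimulation. The changes over 45 and 90 days are secondary and serve Aims 2 and 3.

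**The concern.** In a pain trial, the need to change a patient's treatment is plausibly related to that patient's pain. Someone who worsens on ITN may need more analgesia, may then be withdrawn, and gives no further VAS rating. The patients left for the paired test are those who did better. With no control arm there is nothing for this selection to cancel against, so it passes straight into the mean change at day 45 and day 90.

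The reverse can also happen. A patient who improves may cut other pain therapy, and 5.2 makes no exception for reductions. Removing such patients would count against ITN.

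Replacement makes the problem harder to see, because the final count looks complete. What is at stake is whether a reported 90-day improvement describes everyone who was treated or only those whose treatment did not have to change.

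**Working it through.** **1. The plan's own figures.** Section 10.3 gives 25 patients for 80% power at 0.05 with a 50% fall in pain, and 30 enrolled to cover dropout. It states no baseline mean and no SD of change, so 25 can be neither reproduced nor refuted. A two-sided paired t-test with n = 25 reaches 80% power at a standardised change of 0.584. The dropout allowance is (30 − 25)/30 = 16.7%. Section 3.1 gives 45 patients, so both 30 and 45 are used below.

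**2. Assumed inputs.** The documents give no SD of change, withdrawal rate or withdrawal pattern. Assumed: SD s = 20 or 25 on the 0-100 VAS of 7.1, normal changes, and a worsener or improver defined by a change of more than 10 points. That scale runs "0=extremely uncomfortable, extremely dry and 100=excellent comfort, no dryness", so worsening is a fall in the score; here it is coded as positive. On a 0-10 scale the results are the same with every value divided by 10.

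**3. Shift in the mean.** Suppose there is no true change and worseners are withdrawn with probability p. Let k = 10/s.

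- Share withdrawn: w = p × P(Z > k)
- Mean of those left: −p × s × φ(k)/(1 − w)

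For p = 0.5:

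- s = 20: k = 0.5, P = 0.3085, φ = 0.3521, w = 0.154; shift = −0.5 × 20 × 0.3521/0.846 = −4.2 points
- s = 25: k = 0.4, P = 0.3446, φ = 0.3683, w = 0.172; shift = −0.5 × 25 × 0.3683/0.828 = −5.6 points

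**4. False-positive rate.** Simulation with 40,000 trials per setting, full replacement up to N, and a two-sided t-test on the changes at 0.05. Ranges cover both SDs.

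| Pattern (no true change) | Share of all patients withdrawn | N = 30 | N = 45 |
|---|---|---|---|
| Worseners and improvers equally (30% or 50% of each) | 19-34% | about 5% | about 5% |
| 30% of worseners, 15% of improvers | 14-16% | 6.3-7.5% (both N) | 6.3-7.5% (both N) |
| Worseners only, 10% of them | about 3% | 5.5-5.7% | 5.7-5.8% |
| Worseners only, 30% of them | 9-10% | 10-11% | 13-14% |
| Worseners only, 50% of them | 15-17% | 23-25% | 32-36% |

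In the last row nearly every rejection is a false improvement.

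**5. What replacement contributes.** Repeating the last row without replacement gives the same mean shift (−4.2 and −5.6 points) and false-positive rates of 20-22% (N = 30) and 28-31% (N = 45). Replacement raises the rate a little because it puts more patients around a mean that is already shifted. It does not create the shift.

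**6. The opposite direction.** Withdraw 30% of patients who improve by more than 10 points.

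- True improvement of 10 points (15% of all withdrawn): power falls from 76% to 49% (N = 30, SD 20), 56% to 28% (N = 30, SD 25), 91% to 67% (N = 45, SD 20) and 75% to 40% (N = 45, SD 25).
- The standardised change of 0.584 that 25 patients imply: about 87% to 65% at N = 30.
- A 25-point improvement, if a 50% fall is taken from an assumed pain level of 50: power stays at 99.5% or more.

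The 10-point effect is an assumption and does not come from the plan.

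**The case against.** The strongest reply has four parts.

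**The rule has a purpose and is discretionary.** Without a control arm, keeping patients who add an analgesic credits the new drug to ITN. Section 5.2 says only that withdrawal may follow, and only where the regimen needs to change. This stands as a reason to report ratings before and after a therapy change separately. It does not justify discarding the later outcomes.

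**The large figures need an extreme pattern.** Half of all worseners must leave, nobody else may leave, and together they use about the whole dropout allowance. A two-to-one imbalance gives only 6 to 7.5%. This stands.

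**It is an uncontrolled pilot.** Placebo response and regression to the mean can move a before-after mean whatever happens to withdrawals, so a 5% error rate was never assured. That is true, but the plan tests at 0.05 and aims to show efficacy over 90 days. This source of bias can be removed cheaply, whereas the others cannot without a control.

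**Not all data are lost.** Diaries exist up to withdrawal, and a change first found at a scheduled visit is found where a VAS is due. This limits the exposure mainly to changes between visits, although no rule says that the diary data will be used.

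Two stronger readings are tempting, and the documents do not support them. A reader might infer that 5.2 contradicts 10.2 by expelling the patients whose reduced medication counts as success. Section 7.2 expects those patients at the visits, so this is an overlap that needs one clarifying sentence. A reader might also infer from 5.2 that replacement itself is the source of the bias; step 5 of the working shows that it is not.

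**Conclusion.** The concern holds as a conditional one and should be fixed. Sections 5.2, 7.6 and 10.4, followed as written, allow selection on response in the day-45 and day-90 comparisons, and no other section repairs this. The likelier direction favours ITN. The opposite direction is less certain because 7.2, 10.2 and 10.5 treat reduced pain therapy as an outcome.

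The size cannot be determined from the documents. It is nil if withdrawal is unrelated to pain, small if withdrawal is rare or only moderately imbalanced, and large only in the one-sided case in the last row of the table. All the rates rest on the assumed SD, the normal model and the 10-point cut-off. Quoting 23 to 36% as the expected error rate would go beyond the evidence.

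Nor do the documents support a claim that the primary endpoint is compromised. It is measured in the office at the first visit, before any regimen change during daily use can act. It is largely unaffected provided that first-visit data of withdrawn patients are kept, which the plan should state. Confidence is medium, because the wording is clear but the extent of withdrawal is unknown.

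**What to change.** 1. **Section 5.2.** Record every change in concomitant therapy with direction, date and reason, and keep the patient in follow-up. State that a reduction in pain therapy is an outcome and not a ground for withdrawal.
2. **Section 10.4.** Analyse everyone who received at least one ITN stimulation, and keep all their data, including the first visit, whether or not they are replaced.
3. **Section 7.6.** Collect VAS, OPAS and IDEEL at withdrawal where the patient agrees.
4. **Sections 3.2 and 10.5.** Analyse day 45 and day 90 with all available data, for example by a mixed model for repeated measures. Also report the last rating before any therapy change, because later ratings mix ITN with the new therapy.

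A check of item 4 assumed no true effect, half of the worseners leaving after day 45 because of their recorded day-45 change, and a day-45/day-90 correlation of 0.5 to 0.7. A completers-only test at day 90 rejected in 8 to 16% of trials, and the all-available-data analysis in 4.4 to 4.8%. Those conditions suit the method. They do not cover withdrawal before day 45, which is why item 3 is needed.

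If a sensitivity analysis is wanted for patients who escalated therapy, show a range of unfavourable values. A single penalty such as 20 points is not a bound: in the model above, worseners average s × φ(k)/P, which is 20 × 0.3521/0.3085 = 22.8 points or 25 × 0.3683/0.3446 = 26.7 points.

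The cost is some protocol wording, three existing questionnaires at withdrawal and a little more analysis. The apparent effect may be smaller, and ratings after a therapy change are harder to attribute to ITN. The change has to be made prospectively, because outcomes not collected at withdrawal cannot be recovered.
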